4 PROTOCOL

This study entails contacting original SMART trial treatment arm subjects to seek participation in a data collection of current pain, functional status, and recent treatments. The study will be overseen at each participating study site by a primary investigator and clinical research coordinator (CRC). Telephone visits and data collection will be conducted by an independent study-wide clinical research nurse (CRN).

Five-Plus Year Follow-up Visit

Study subjects who were randomized to the treatment arm and received treatment in the original SMART trial are eligible to participate in this 5+ year follow-up data collection. Each study site will make initial contact with the prior study patient and discuss the SMART 5+ year data collection and discern if the prior subject is interested in participating. Informed consent will be obtained, and the same unique subject ID # used in the SMART trial will be assigned to the subject. Study participant logs will include subject ID, date(s) of contact, and date of consent/decline to participate and will be maintained by the study site and independent CRN.

Upon subject agreement to participate in the study, the CRC will forward subject contact information to the independent CRN who will then ensure informed consent and schedule the telephone study visit. The independent CRN will perform the telephone study visit and will be responsible for collection of all data elements on source document worksheets

including administering a verbal ODI-based questionnaire, collecting a numeric rating of low back pain over the past 7 days, an assessment of narcotic medications for low back pain taken in the past 30 days, injections for low back pain in the last 12 months, and surgical interventions since the subject's Intracept Procedure, and patient satisfaction with the Intracept Procedure. The independent CRN will enter all data elements into the clinical database.

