7.4 Narcotic Medications & Injections

Patient-reported low back narcotic usage will be captured at the 5+ year follow up visit. Drug type, prescribed dosage, and average daily dose for the last 30 days will be documented on the source document worksheet.

Patient-reported injections within the last 12 months will be collected. Date, type, and location for each injection will be recorded.

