7.5 Surgical Interventions

Surgical interventions performed since the Intracept Procedure will be captured. Date, type and location of each intervention will be recorded.

Interventions will be adjudicated by an independent reviewer.

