9.3 Confidentiality

Subject medical information obtained for this study is confidential, and disclosure to third parties other than those authorized for the study and IRB/regulatory oversight is prohibited. Subjects will be only identified by the unique study number that the subject used during the SMART study. Data will be de-identified in a manner compliant with HIPAA regulations.

Upon the subject's agreement to participate, the independent CRN will schedule and conduct the telephone study visit. Subject's permission for the use of records for supplemental data and data verification purposes will be obtained prior to accessing subject's medical records.

Data generated by this study must be available for inspection upon request by representatives of the FDA, national and local health authorities, the Sponsor or its designee, and the IRB for the study site, if appropriate.

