#### Opioids, Injections, and Interventions

Patient treatments including opioid use in the past 30 days (prior to the study visit), injections in the past 12 months (prior to study visit), and interventions post the Intratect procedure will be collected on the case report form (CRF).

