### **2.6 Endpoint Adjudication**

An independent orthopaedic surgeon will review medical records and radiologic images to determine diagnosis (pain location, etiology, and nature) resulting in an intervention (procedure and/or injections). All interventions will be adjudicated as either a treatment failure (ongoing or exacerbated CLBP of similar location, etiology and nature/severity to the pre-Intratect treatment pain) or not related (different location, etiology, or nature/severity).

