Mean # of injections per subject in 12 months prior to baseline	% (n/N)
Mean # of injections per subject in 12 months prior to 5+ year post treatment visit	% (n/N)
Time to first injection for low back pain in same location post Intracept Procedure	Mean + SD, Median, Range

	CD_3012_Rev B Five-Plus Year Follow-Up of SMART Trial Statistical Analysis Plan	Date Effective: November 5, 2019 Page 18 of 21
---	--	---

Table 13 – Surgical Interventions	
	SMART 5+ Yr Follow-up Subjects N = XX
Number (%) of subject reporting a procedure	% (n/N)
Number of procedures	% (n/N)
Re-intervention Rate over Time	
1 Year	S% (95% CI)
2 Year	S% (95% CI)
5 Year	S% (95% CI)
Type of procedure:	
Discectomy	% (n/N)
Lumbar fusion	% (n/N)
RF Ablation	% (n/N)
Other	% (n/N)
At the same level of Intracept treatment?	
Yes	% (n/N)
No	% (n/N)
Time to intervention (post Intracept procedure)	Mean + SD, Median, Range
Same etiology and level as Intracept treatment	Mean + SD, Median, Range
Different etiology or level from Intracept treatment	Mean + SD, Median, Range

Table 14 – Pain Status at 5 + Years	
	SMART 5+ Yr Follow-up Subjects N = XX
Pain Status	
Constant	% (n/N)
Intermittent	% (n/N)
No Pain	% (n/N)
Experiencing Pain	
Same location as prior to Intracept Procedure	% (n/N)
Different location from prior to Intracept Procedure	% (n/N)
Same nature as prior to Intracept Procedure	% (n/N)
Different nature from prior to Intracept Procedure	% (n/N)
Time (per year) effect on VAS in INTRACEPT group	Mean, N, 95% CI, rm F-test p (Ho: time=0)

	CD_3012_Rev B Five-Plus Year Follow-Up of SMART Trial Statistical Analysis Plan	Date Effective: November 5, 2019 Page 19 of 21
---	--	---

Table 15 – Durability at 5 + Years	
	SMART 5+ Yr Follow-up Subjects N = XX
Number (%) of subjects reporting a re-intervention (lumbar procedure adjudicated as same location and etiology as Intracept procedure)	% (n/N)
Number (%) of subjects reporting actively using opioids (defined as > 25% of total prescribed dosage in 30 days prior to visit)	%(n/N)
Number (%) of subjects reporting low back pain injections in same treatment location as Intracept.	% (n/N)
Number (%) of subjects reporting less than 2 point decrease in pain (in same location) compared to baseline	% (n/N)
Number (%) of subjects reporting less than 10 point decrease in ODI compared to baseline	% (n/N)

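### Table 12's time-to-first-injection row cannot be derived from the 12 months of injection history that the visit collects, and three baseline entries are not defined like their follow-up counterparts (minor)

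*SAP*

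**What the plan says.** The last injection row of Table 12 (SAP Appendix A) is "Time to first injection for low back pain in same location post Intracept Procedure", with mean, SD, median and range as the cell content. The clock starts at the procedure.

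The visit looks back a much shorter way. Protocol section 4 lists "injections for low back pain in the last 12 months, and surgical interventions since" the procedure, which puts two different look-back periods side by side. Protocol section 7.4 states "Patient-reported injections within the last 12 months will be collected", with date, type and location for each. SAP section 2.5 words the case report form entry as "injections in the past 12 months (prior to study visit" and lists it apart from interventions after the procedure. For surgery the full period is explicit in Protocol section 7.5: "Surgical interventions performed since the Intracept Procedure will be captured".

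Two passages mention other sources. SAP section 2.6 says "An independent orthopaedic surgeon will review medical records and radiologic images to determine diagnosis" behind an intervention, and there counts injections among interventions. Protocol section 9.3 provides for "permission for the use of records for supplemental data and data verification purposes".

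Table 12 also sets baseline against follow-up for opioid use, opioid dose, the share of subjects injected and the mean number of injections. SAP section 4.2 makes within-subject comparison of baseline with 5+ years the default.

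**The concern.** A statistic that starts at the procedure is requested from a history that starts 12 months before the visit. A programmer who fills the row from visit data will produce a number, and nothing in the shell will show that it is wrong. For any one subject the recorded value is either right or too late, so the error runs in the direction that makes the treatment look more durable. Subjects whose injections all came earlier drop out of the row and look as if they had never been injected.

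The paired rows raise a smaller question. Given the default in SAP section 4.2, readers will take them as change in utilisation. Where the two time points follow different rules, or the baseline rule is not given, part of an apparent change may come from the definitions.

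**Working it through.** The plan gives no figure for this row, so there is nothing to reproduce. Step 1 follows from the windows alone. Steps 2 to 4 and 6 are illustrations on assumed rates.

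**Inputs.** The look-back is 1 year (Protocol sections 4 and 7.4; SAP section 2.5). Length of follow-up F is not given. The study is described as 5+ years, but Table 8 reports the share with at least 5 years, so shorter follow-up is possible; I assume F = 4 to 8. The yearly injection probability p is not given; I assume 5% to 20%, constant over time. That SMART holds injection dates for its first 24 months is also an assumption.

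**1. Floor.** The earliest injection the visit can record is at F-1 years: 4 years at F = 5, where the window covers 1/5 = 20% of the time since the procedure, and 7 years at F = 8 (1/8 = 12.5%).

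**2. Share of true first injections that fall in the collected year.** This is [(1-p)^(F-1) - (1-p)^F] / [1 - (1-p)^F]. At F = 5 and p = 10%: (0.6561 - 0.5905) / (1 - 0.5905) = 0.0656 / 0.4095 = 16.0%. If 24 months of SMART dates were added, the share still uncovered would be [(1-p)^2 - (1-p)^(F-1)] / [1 - (1-p)^F] = (0.8100 - 0.6561) / 0.4095 = 37.6%.

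| F (years) | Floor (years) | In collected year, p = 5 / 10 / 20% | Uncovered even with 24 months of SMART dates |
|---|---|---|---|
| 4 | 3 | 23.1 / 21.2 / 17.3% | 24.3 / 23.6 / 21.7% |
| 5 | 4 | 18.0 / 16.0 / 12.2% | 38.9 / 37.6 / 34.3% |
| 6 | 5 | 14.6 / 12.6 / 8.9% | 48.6 / 46.8 / 42.3% |
| 7 | 6 | 12.2 / 10.2 / 6.6% | 55.5 / 53.4 / 47.8% |
| 8 | 7 | 10.4 / 8.4 / 5.0% | 60.7 / 58.2 / 51.7% |

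With h = -ln(1-p), the true median among those injected is -ln(1 - 0.5[1 - (1-p)^F]) / h. It runs from 1.57 years (F = 4, p = 20%) to 3.59 years (F = 8, p = 5%), against floors of 3 and 7 years.

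**3. Wrong first dates.** Among subjects injected in the last year, the share with an earlier post-procedure injection is 1 - (1-p)^(F-1) if years are independent: 14.3% (F = 4, p = 5%) to 79.0% (F = 8, p = 20%). It is 0% if nobody is injected twice and 100% if the same subjects are injected every year.

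**4. Censoring.** Even with complete dates, a median among the injected misleads. At F = 5 and p = 10%, 41.0% are ever injected and their median is 2.17 years. The median for all subjects is ln 2 / h = 6.58 years, beyond follow-up and so not reached on a Kaplan-Meier curve.

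**5. Paired rows.**

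| Measure | Baseline | Follow-up |
|---|---|---|
| Opioid use | No threshold, no window (Table 12) | Active use, above 25% of dosage, 30 days (SAP 3.1.2; Tables 12, 15) |
| Opioid dose | 7 days (Table 6); none printed in Table 12 | 30 days (Protocol 7.4); none printed in Table 12 |
| Share injected | No window | 12 months |
| Mean number of injections | 12 months | 12 months |

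The first three pairs do not match or cannot be shown to match. The fourth does.

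**6. Possible size of a definition effect.** Suppose baseline counts any opioid use in the same window, nothing truly changes, and a share s of users is at or below 25%. The shown relative change is then -s: 0, -10, -20 or -30% for s = 0, 10, 20 or 30%. It is zero if baseline used the same rule, and a different baseline window could move it either way. If prior injections at baseline covered L years with independent years, the baseline share would be 1 - (1-p)^L. For L = 2 and 3 that is 9.8% and 14.3% against 5% at follow-up, or 36.0% and 48.8% against 20%. There is no effect if baseline also means 12 months, or if the same subjects are injected every year.

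**The case against.** The strongest reply is that the plan does not tie this row to visit data. SAP section 2.6 counts injections among adjudicated interventions and uses medical records, SAP section 2.5 collects interventions after the procedure, and Protocol section 9.3 allows records as supplemental data. Table shells seldom name a source for each row. This stands as far as it goes: a source may exist, and it would be too strong to infer that the row can never be filled. But SAP section 2.5 gives injections their own 12-month entry. The record review serves to classify interventions; it is not described as a search for every injection since the procedure.

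The second reply is that little depends on the row. Time to first injection is not an endpoint in Protocol section 5.2 or SAP section 3.1.2, and Table 12 has no change row and no p-value. SAP section 4.1 allows inferential statistics for secondary variables, but none is planned in this shell. This reply stands and sets the severity.

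Third, the summary format is the SAP's own. Table 13 has a row group, "Re-intervention Rate over Time", with 95% confidence intervals, but it also reports time to intervention as mean, SD, median and range. So Table 13 is not a clean contrast; the censoring remark applies there too.

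Fourth, a reader might infer that every baseline injection row is mismatched, or that any fall in opioid use would be an artefact. The documents support neither. The mean-count rows already share a 12-month window, and the baseline opioid rule is unstated, so it may be the same rule.

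**Conclusion.** The point holds and is minor. Visit data cannot give time to first injection since the procedure: no value can be below F-1 years, and a recorded value can be too late but never too early. That conclusion needs no assumed rate. It is a statement about each subject; where follow-up lengths differ, a pooled mean also depends on which subjects drop out of the row. The percentages rest wholly on assumed values of F and p and show only that the shortfall would be large under ordinary rates.

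The baseline gaps concern opioid use, opioid dose and the share of subjects injected. They limit how far Table 12 can be read as change; they do not show that a change would be false.

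It would be wrong to carry the point further. The primary ODI test does not use these rows. The endpoint proportions are defined at follow-up, and the composite's injection criterion uses the same 12 months that the visit collects. The SAP's opioid denominator is total dosage in section 3.1.2 and in the success definition under Table 15, but total prescribed dosage in a row of Table 15. That wording belongs to the composite definition and should be reconciled as a separate point.

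**What to change.** Delete the time-to-first-injection row, or name a source that covers the whole period since the procedure. If it stays, report Kaplan-Meier estimates with subjects without an injection censored at their visit, and treat Table 13's time-to-intervention row the same way.

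For the paired rows:
- Use a 12-month window at both times for the share of subjects injected, as the mean-count rows already do.
- State the threshold and window behind the baseline opioid-use row.
- Keep the prespecified above-25% row at follow-up and add a row for any opioid use for low back pain in the last 30 days, from data already collected under Protocol section 7.4.
- Footnote the 7-day baseline against the 30-day follow-up window for opioid dose. The added row does not remove that difference, and if baseline use was also recorded over 7 days, the footnote should cover it as well.

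The same edit can correct two clerical slips: the cell formats of the subject-count and mean-count injection rows are swapped, and the rows sit under an epidural heading although the endpoint covers injections generally.

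Cost: SAP wording and table-shell edits, with no new data if the row is deleted. Deletion loses one descriptive item; keeping the row means record review back to the procedure. The any-use row may make the comparison with baseline look less favourable.

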## 2. STUDY DESIGN

### 2.1 Overall Study Design

This study is a post-market, non-interventional, data collection of the long term (5 + year) follow-up in the 133 treatment arm subjects in the SMART trial in the U.S. The study will be conducted at the same thirteen U.S. study sites where the procedures occurred.

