#### 4. STATISTICAL AND ANALYTICAL PLANS

##### 4.1 General Methodology

The SMART Five Plus Year Follow-up Study analysis will be performed when all US SMART treatment arm subjects have been approached to participate in the study, and all subjects who consented to participate, have completed their 5+ year follow-up study visit.

	CD_3012_Rev B Five-Plus Year Follow-Up of SMART Trial Statistical Analysis Plan	Date Effective: November 5, 2019 Page 9 of 21
---	---	---

The number of subjects in the analysis and reasons for withdrawal will be summarized in a CONSORT flowchart. All subjects consenting to participate in the long term follow-up study will be reported as observed. No imputations are planned for missing data.

All statistical processing will be performed by Technomics Research LLC. The standard operating procedures (SOPs) of Tehcnomics Research LLC will be followed in the creation and quality control of all data displays and analyses. Analyses will be conducted using SAS® software Version 9.3 or later unless otherwise stated.

Statistical tests will be two-sided and will be performed at the 0.05 level of significance.

Descriptive statistics will be used for secondary endpoints and will include the number and percentage of subjects in each category. For continuous parameters, descriptive statistics will include n (number of subjects), mean, SD, median, minimum, and maximum. Appropriate inferential statistics will be used for the primary and secondary efficacy variables.

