#### **4.4 Analyses and Data Monitoring**

##### **4.4.1 Demographic and Other Baseline Characteristics**

Demographic and baseline characteristics responses will be summarized with descriptive statistics for the observed study population. A comparison of baseline demographics, co-morbidities, medical history and baseline values for ODI and VAS of the observed study population will be performed to the SMART trial full treatment arm group.

Additionally, ODI, VAS and AE histories will be compared to demonstrate that the LTFU subjects are missing at random and are not systematically different from the retained subjects.

	CD_3012_Rev B Five-Plus Year Follow-Up of SMART Trial Statistical Analysis Plan	Date Effective: November 5, 2019  Page 10 of 21
---	--	---

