#### **4.4.2 Primary Efficacy Analysis**

The efficacy analysis will be conducted all consented treated subjects with a 5+ year study visit. Results will be reported for observed data only; missing values will not be imputed.

The primary analysis will test the mean improvement in ODI from baseline to 5+ years as an intra-patient comparison. The mean change will be analyzed with an ANCOVA with a covariate of baseline ODI score. See Appendix A - Table 8.

If  $p \leq 0.05$  then it may be concluded that a significant functional improvement was demonstrated in axial low back pain subjects treated with the Intracept procedure and that the treatment is durable to mean follow-up for the long term study.

A comparison will be made between the ITT (as treated cohort) and a Intracept only treated cohort (with those subjects that had additional procedures such as RF Ablation, microdiscectomy, fusion, etc. removed).

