## 5. APPENDIX A – ANALYSIS TABLES

Table 1 - Summary of Screening (Enrolled Subjects)	
	SMART 5+ Year US Treatment Arm Cohort (N=132)
Enrolled (Consented)	% (n/N)
Study Non-Participation Reason	% (n/N)
Declined Participation	% (n/N)
Subject Withdraw Consent	% (n/N)
LTFU	% (n/N)
Death	% (n/N)
Other	% (n/N)

Table 2 - Demographic Information			
Characteristic	SMART Treated Subjects in 5+ Yr Follow-up N = XX	SMART Treated Subjects Not in 5+ Year Follow-up N = XX	t-test of Means or Exact Test of Proportions
Age (years)	Mean + SD, Median, Range	Mean + SD, Median, Range	
Gender:			
Male	% (n/N)	% (n/N)	
Female	% (n/N)	% (n/N)	

Table 3 – Baseline Social/Socioeconomic/Work History			
Characteristic	SMART Treated Subjects in 5+ Yr Follow-up N = XX	SMART Treated Subjects Not in 5+ Year Follow-up N = XX	t-test of Means or Exact Test of Proportions
Baseline Working Status			
Working	% (n/N)	% (n/N)	
Working Full-Time	% (n/N)	% (n/N)	
Working Part-Time	% (n/N)	% (n/N)	
Not Working	% (n/N)	% (n/N)	
Short-Term Disability	% (n/N)	% (n/N)	
Not Working Due to Back Pain	% (n/N)	% (n/N)	
Unemployed	% (n/N)	% (n/N)	
Retired	% (n/N)	% (n/N)	
Other	% (n/N)	% (n/N)	
Time since last worked (for subject not working due to back pain)	Mean + SD, Median, Range	Mean + SD, Median, Range	

	CD_3012_Rev B Five-Plus Year Follow-Up of SMART Trial Statistical Analysis Plan	Date Effective: November 5, 2019 Page 13 of 21
---	---	--

Table 4 – Baseline Characteristics			
Characteristic	SMART Treated Subjects in 5+ Yr Follow-up N = XX	SMART Treated Subjects Not in 5+ Year Follow-up N = XX	t-test of Means
Baseline ODI	Mean + SD, Median, Range	Mean + SD, Median, Range	
Baseline VAS	Mean + SD, Median, Range	Mean + SD, Median, Range	

Table 5 – Baseline Low Back Pain History			
Characteristic	SMART Treated Subjects in 5+ Yr Follow-up N = XX	SMART Treated Subjects Not in 5+ Year Follow-up N = XX	t-test of Means or Exact Test of Proportions
Length of Time Experience LBP			
< 6 months	% (n/N)	% (n/N)	
6 months to < 1 year	% (n/N)	% (n/N)	
1 year to < 2 years	% (n/N)	% (n/N)	
2 years to < 3 years	% (n/N)	% (n/N)	
3 years to < 5 years	% (n/N)	% (n/N)	
> 5 years	% (n/N)	% (n/N)	
# of days a Week Subject Experiences Low Back Pain	Mean + SD, Median, Range	Mean + SD, Median, Range	
Modic Type by Level & Endplate			
L3 Superior Endplate	% (n/N)	% (n/N)	
Modic I	% (n/N)	% (n/N)	
Modic II	% (n/N)	% (n/N)	
L3 Inferior Endplate	% (n/N)	% (n/N)	
Modic I	% (n/N)	% (n/N)	

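### SAP Table 13 estimates 1-, 2- and 5-year re-intervention only in subjects who took the 5+ year call, so entry to the early risk sets depends on a later event.

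*SAP*

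**What the plan says.** Table 13 (SAP Appendix A, Surgical Interventions) has one column, headed "SMART 5+ Yr Follow-up Subjects". Under the row "Re-intervention Rate over Time" it lists 1, 2 and 5 years, each to be filled as S% (95% CI). SAP sections 4.4.3.1 to 4.4.3.5 do not describe this analysis, so no estimator, risk set or censoring rule is given.

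The text agrees with the column heading. SAP 4.1 states: "All subjects consenting to participate in the long term follow-up study will be reported as observed. No imputations are planned for missing data". SAP 4.4.2 defines the efficacy set: "The efficacy analysis will be conducted all consented treated subjects with a 5+ year study visit". Protocol section 4 has the research nurse collect surgical interventions at the telephone visit, looking back to the Intracept procedure (also Protocol 7.5).

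Non-participants do appear elsewhere. Table 1 counts them by reason (declined, withdrew consent, lost, died, other). Tables 2-7 and 11 have a column "SMART Treated Subjects Not in 5+ Year Follow-up N = XX". These tables cover baseline items, levels treated and SMART outcomes for ODI and VAS. None has a re-intervention row. SAP 4.4.1 adds that "ODI, VAS and AE histories will be compared", but gives no table for the AE comparison and does not link it to Table 13.

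The treated cohort is given as "133 treatment arm subjects in the SMART trial in the U.S" in SAP 2.1 and as N=132 in Table 1.

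**The concern.** Time at risk for re-intervention starts at the procedure. Membership of the Table 13 column is settled only at the call, years afterwards. Restricting the 1- and 2-year rates to call attendees therefore conditions early risk on a later event. A subject re-operated at 14 months who later declined the call would be absent from the 2-year rate, although followed for the relevant period.

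This differs from a missing 5-year ODI or pain score. Follow-up that was observed is set aside, and counting a subject up to last contact is not imputation, so the no-imputation rule does not require the exclusion.

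At stake is how three rows are read. A reader will take them as re-intervention rates after treatment, when they are rates among people who later took part in a follow-up. If taking part is related to having had further surgery, the rates are biased, and the confidence intervals will not show it.

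**Working it through.** The documents give no re-intervention rate and no expected attendance, so there is no planned figure to reproduce. Apart from the 133, every input below is an assumption.

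**Step 1. Who is in the early risk sets.** The Table 13 heading, SAP 4.1 and SAP 4.4.2 all restrict to consented subjects, the last to those with a visit. No section adds non-attendees, even as censored subjects.

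**Step 2. Simple proportions at 2 years.** Let N = 133, with 100 attendees (assumed), 33 non-attendees, and 4 attendee events (assumed). Let x be the events that SMART recorded by 2 years in non-attendees.

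- Table 13: 4/100 = 4.0%.
- All treated: (4 + x)/133.

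| x | Risk in non-attendees | All treated |
|---|---|---|
| 0 | 0/33 = 0% | 4/133 = 3.0% |
| 1 | 1/33 = 3.0% | 5/133 = 3.8% |
| 3 | 3/33 = 9.1% | 7/133 = 5.3% |
| 5 | 5/33 = 15.2% | 9/133 = 6.8% |

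Equal risk would mean 33 × 0.04 = 1.3 events, so x = 1 is close to the no-bias case. With N = 132 the last column is the same to one decimal (4/132 = 3.0%, 5/132 = 3.8%, 7/132 = 5.3%, 9/132 = 6.8%).

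**Step 3. Set against sampling error.** The Wilson 95% interval for 4/100 has centre (0.04 + 3.8416/200)/1.0384 = 0.0570 and half-width 1.96 × √(0.04 × 0.96/100 + 3.8416/40000)/1.0384 = 0.0414, that is 1.6% to 9.8%. The shifts in Step 2, from −1.0 to +2.8 points, lie inside it. They are systematic, however, and the interval does not represent them.

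**Step 4. What an all-treated Kaplan-Meier estimate repairs.** Assume 60% attendance (80 attendees, 53 not), a constant hazard with 10% re-intervention at 5 years in attendees, a hazard ratio HR for non-attendees against attendees, and non-attendees followed in SMART to 24 months and then censored.

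- Attendees: 2-year risk 1 − 0.9^0.4 = 4.1%; 5-year risk 10.0%.
- Non-attendees: 2-year risk 1 − 0.9^(0.4·HR); 5-year risk 1 − 0.9^HR.
- All treated at 2 years: the average of the two risks, weighted 80:53.
- Expected all-treated Kaplan-Meier at 5 years: 1 − (1 − 2-year mixture) × 0.9^0.6, because only attendees remain after 24 months; 0.9^0.6 = 0.9387.

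| HR | Non-attendees, 2 y | All treated, 2 y | Kaplan-Meier, 5 y | True all treated, 5 y |
|---|---|---|---|---|
| 0.5 | 2.1% | 3.3% | 9.2% | 8.1% |
| 1 | 4.1% | 4.1% | 10.0% | 10.0% |
| 3 | 11.9% | 7.2% | 12.9% | 16.8% |

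For HR 3: (80 × 4.13 + 53 × 11.88)/133 = 7.2%; 1 − 0.9278 × 0.9387 = 12.9%; (80 × 10 + 53 × 27.1)/133 = 16.8%. At 90% attendance (120 and 13) and HR 3, the 2-year figure is (120 × 4.13 + 13 × 11.88)/133 = 4.9%.

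Table 13 would show about 4.1% and 10.0% in every row. The all-treated estimate recovers the 2-year rate under these assumptions, but closes only part of the gap at 5 years.

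**Step 5. Censoring among attendees.** Table 8 has a row for the percentage with at least 5 years of follow-up, so the plan allows for attendees seen before 5 years. They too need a censoring rule in the 5-year entry.

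**The case against.** The strongest reply has four parts.

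*The documents do not show that anything is dropped.* SAP section 1 mentions ODI, VAS, opioid and injection results in SMART, and SAP 4.4.1 mentions AE histories. Nothing says that SMART recorded surgical re-interventions. This stands. A reader might infer that the sponsor holds such events and leaves them out. The text supports only that any recorded in SMART would be left out.

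*The direction is unknown.* A reader might infer that Table 13 must be too low, on the view that people re-operated early would not join. No passage supports that. With equal hazards the cost is precision only, and with a lower hazard in non-attendees Table 13 overstates the rate. This stands.

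*This is the study-wide restriction to attendees seen in one table, and that restriction is disclosed.* Partly right. The column is labelled, a CONSORT flowchart is planned, and Tables 2-7 and 11 compare attendees with non-attendees. Those comparisons cannot show whether re-intervention differs. For 1- and 2-year rates, SMART follow-up may already supply what the call cannot. The rows are also descriptive, with no success criterion attached.

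*An all-treated estimate would be a different endpoint.* SAP 2.6 adjudicates from medical records and images, and Protocol 9.3 requires the subject's permission for records. Early events in non-attendees would therefore be unadjudicated and could not be set against the adjudicated count in Table 15. This stands as a limit. Table 13's own first row, though, counts subjects reporting a procedure without an adjudication condition, so an unadjudicated estimate fits that table.

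**Conclusion.** The point holds as a cheap improvement. The Table 13 heading and SAP 4.1 and 4.4.2 put only call attendees in the 1- and 2-year risk sets, nothing elsewhere in the SAP corrects this, and S% has no named estimator. If S% is a simple proportion, the same selection applies.

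The size cannot be derived from the documents. In the 100-attendee illustration, 4.0% in Table 13 corresponds to 3.0% to 6.8% in all treated subjects for 0 to 5 non-attendee events. This rests on assumed attendance and assumed event counts.

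Two further readings go too far. Re-intervention is not the study's only long-term event measure: Table 12 includes time to first injection. Nor would the all-treated estimate settle the 5-year rate. Beyond the last SMART visit it rests on attendees and on censoring being unrelated to later re-intervention.

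**What to change.** In the SAP:

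1. Name the estimator behind S% in Table 13, with its time origin and censoring rule, including for attendees seen before 5 years.
2. Add an estimate of any low back procedure, timed from the Intracept procedure, in all US treated subjects. Use SMART follow-up and AE records for non-attendees and censor them at last SMART contact. Either treat death as a competing event or censor at death, and say which.
3. Show numbers at risk at 1, 2 and 5 years.
4. Keep the attendee-only and adjudicated results alongside.
5. State that beyond the last SMART visit the estimate rests on attendees and assumes non-informative censoring.
6. Reconcile 133 (SAP 2.1) with 132 (Table 1), since this is the denominator.

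The cost is SAP wording and one further analysis, with no new patient contact. The downside is that early events in non-attendees would be unadjudicated. The analysis also depends on SMART having captured interventions, so the sponsor should confirm that first. If SMART did not, items 1 and 3 and a plain statement of the selection are what remains.
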